# 6.4 Annex 2c – Technology Readiness Index (TRI)

Please indicate how much you agree with the following statements.

	Strong ly disagr ee	Somewh at disagree	Neutral	Somewh at agree	Strong ly agree
1. New technologies contribute to a better quality of life					
2. Technology gives me more freedom of mobility					
B. Technology gives people more control over their daily lives					
B. Technology makes me more productive in my personal life					

	Strong ly disagr ee	Somewh at disagree	Neutral	Somewh at agree	Strong ly agree
B. Other people come to me for advice on new technologies					
B. In general, I am among the first in my circle of friends to acquire new technology when it appears					
B. I can usually figure out new high-tech products and services without help from others					
B. I keep up with the latest technological developments in my areas of interest					

	Strong ly disagr ee	Somewh at disagree	Neutral	Somewh at agree	Strong ly agree
9. When I get technical support from a provider of a high-tech product or service, I sometimes feel as if I am being taken advantage of by someone who knows more than I do					

10. Technical support lines are not helpful because they don't explain things in terms I understand			
11. Sometimes, I think that technology systems are not designed for use by ordinary people			
12. There is no such thing as a manual for a high- tech product or service that's written in plain language			

#### TRI (cont.)

	Strong ly disagr ee	Somewh at disagree	Neutral	Somewh at agree	Strong ly agree
13. People are too dependent on technology to do things for them					
14. Too much technology distracts people to a point that is harmful					
15. Technology lowers the quality of relationships by reducing personal interaction					
16. I do not feel confident doing business with a place that can only be reached online					

# 6.5 Annex 2d – eHealth Literacy (eHEALS)

Please indicate your level of agreement with each of the following statements using the scale provided below.

Please select a single option for each statement

-2	-1	0	+1	+2
Strongly	Somewhat	Neutral	Somewhat	Strongly
disagree	disagree		agree	agree

1. I know how to find helpful health resources on the Internet	-2	-1	0	+1	+2 □
2. I know how to use the Internet to answer my health questions	-2	-1	0	+1	+2
3. I know what health resources are available on the internet	-2	-1	0	+1	+2
4. I know where to find helpful health resources on the internet	-2	-1	0	+1	+2
5. I know how to use the health information I find on the Internet to help me	-2	-1	0	+1	+2
6. I have the skills I need to evaluate the health resources I find on the Internet	-2	-1	0	+1	+2
7. I can tell high quality from low quality health resources on the Internet	-2	-1	0	+1	+2
8. I feel confident in using information from the Internet to make health decisions	-2	-1	0	+1	+2

# 6.6 Annex 3 – EQ5D-5L (UK English sample version)

Under each heading, please tick the ONE box that best describes your health TODAY.

#### MOBILITY

I have no problems in walking about	
I have slight problems in walking about	
I have moderate problems in walking about	
I have severe problems in walking about	
I am unable to walk about	

#### SELF-CARE

I have no problems washing or dressing myself	
I have slight problems washing or dressing myself	
I have moderate problems washing or dressing myself	
I have severe problems washing or dressing myself	
I am unable to wash or dress myself	

#### USUAL ACTIVITIES (e.g. work, study, housework, family or

leisure activities)	
I have no problems doing my usual activities	
I have slight problems doing my usual activities	
I have moderate problems doing my usual activities	
I have severe problems doing my usual activities	
I unable to do my usual activities	

#### PAIN / DISCOMFORT

I have no pain or discomfort	
I have slight pain or discomfort	
I have moderate pain or discomfort	
I have severe pain or discomfort	
I have extreme pain or discomfort	

#### **ANXIETY / DEPRESSION**

I am not anxious or depressed	
I am slightly anxious or depressed	
I am moderately anxious or depressed	
I am severely anxious or depressed	
I am extremely anxious or depressed	
#### (EQ5D-5L, cont.)

- We would like to know how good or bad your health is TODAY.
- This scale is numbered from 0 to 100.
- 100 means the best health you can imagine.

0 means the worst health you can imagine.

- Mark an X on the scale to indicate how your health is TODAY.
- Now, please write the number you marked on the scale in the box below.

YOUR HEALTH TODAY =

# 6.7 Annex 4 – Health-related behaviour

The questions related to health-related behaviour originate from different scales (e.g. Stanford research instruments) and are slightly modified in order to fit to the study setting and population.

### 1: Do you smoke cigarettes?

(Please tick one box only)

- ▲ Yes, I do  $\rightarrow$  go to question I2
- 🔺 No, I never did
- No, I don't but I did in the past

➔ When did you stop smoking? Month: \_\_\_ Year: \_\_.\_\_.

2: How many cigarettes on average do you smoke per day?

(Please fill in your average daily cigarette consumption)

On average, I smoke \_\_\_\_\_ cigarettes per day

- 3: Do you currently use any of the following tobacco or nicotine products; chewing tobacco or snuff, cigars, tobacco pipes, clove cigarettes or bidis, e-cigarettes, nicotine replacement products such as gum or patch or any other tobacco products besides cigarettes? (Please tick each box that applies to you)
  - Yes, I chew or snuff tobacco
  - 🔺 Yes, I smoke cigars
  - Yes, I smoke tobacco pipes
- Yes, I smoke clove cigarettes or bidis
- Yes, I smoke e-cigarettes
- Yes, I use nicotine replacement products
- Other: \_\_\_\_\_
- 🕳 No

4: Please think about a normal week. How many units of alcohol do you drink per week (one unit corresponds to 1 beer, 1 glass of wine or 4cl. of spirits)?

(Please fill in the number of units)

units per week

5: Please think about a normal week. How many portions of vegetables do you eat per week?

Vegetables are all cooked and uncooked vegetables; salads; and boiled, baked and mashed potatoes. Do not count French fries or chips.

One portion is 80g of vegetables corresponding to e.g. two broccoli spears, one medium tomato, three heaped tablespoons of beans or carrots, etc.)

(Please fill in the number of portions)

portions per week

#### 6: Please think about a normal week. How many portions of fruits do you eat per week? Include fresh, frozen or canned fruits.

One portion is 80g of fruit corresponding to e.g. two plums, seven strawberries, one apple, one slice of pineapple, etc.) (Please fill in the number of portions)

portions per week

# 7: During the past week (even if it was not a typical week for you), how much total time (for the entire week) did you spend on each of the following activities?

How much time during the past week…	None	Less than 30 minutes / week	30-59 minutes / week	1-3 hours / week	More than 3 hours / week
Stretching or strengthening exercises (range of motion, weights, etc.)					
Walk for exercise, hiking, Nordic walking					
Swimming or aquatic exercise					
Bicycling (including stationary exercise bikes)					
Other aerobic exercise equipment (stairmaster, rowing skiing machine, etc.)					
Other aerobic exercise: Please specify:					

(Please make one cross on each line)

#### 8: Do you walk outside?

(with walking outside we mean walking to go shopping or doing other daily activities like visiting someone; we do not mean: a walking tour; Please tick one box only).

#### 9: How many times did you walk during the past two weeks?

(with walking outside we mean walking to go shopping or doing other daily activities like visiting someone; we do not mean: a walking tour; Please fill in the correct number).

I walked |\_\_||\_\_| times in the past two weeks

#### 10: How long did you usually walk each time?

(with walking outside we mean walking to go shopping or doing other daily activities like visiting someone; we do not mean: a walking tour; Please fill in the correct number).

I usually walk |\_\_||\_\_| hours and |\_\_||\_\_| minutes

# 11: Please think about the past two weeks. Did your overall activity level change as compared to the rest of the year? (Please tick one box only)

- No, my activities did not change at all.
- Yes, I am more physically active than before.
- Yes, I am less physically active than before.
- 🛋 I don't know

# 6.8 Annex 5 – Self-Efficacy

For each of the following questions, please choose the number that corresponds to your confidence that you can do the tasks regularly at the present time.

(Please select a single option for each statement)

# 1: How confident are you that you can keep the fatigue caused by your disease from interfering with the things you want to do?

Not at all confident	1	2	3	4	5	6	7	8	9	10	Totally confident
----------------------	---	---	---	---	---	---	---	---	---	----	-------------------

# 2: How confident are you that you can keep the physical discomfort or pain of your disease from interfering with the things you want to do?

Not at all confident	1	2	3	4	5	6	7	8	9	10	Totally confident
----------------------	---	---	---	---	---	---	---	---	---	----	-------------------

# 3: How confident are you that you can keep the emotional distress caused by your disease from interfering with the things you want to do?

Not at all confident	1	2	3	4	5	6	7	8	9	10	Totally confident
----------------------	---	---	---	---	---	---	---	---	---	----	-------------------

# 4: How confident are you that you can keep any other symptoms or health problems you have from interfering with the things you want to do?

Not at all confident	1	2	3	4	5	6	7	8	9	10	Totally confident
----------------------	---	---	---	---	---	---	---	---	---	----	-------------------

# 5: How confident are you that you can do the different tasks and activities needed to manage your health condition so as to reduce your need to see a doctor?

Not at all confident	1	2	3	4	5	6	7	8	9	10	Totally confident
----------------------	---	---	---	---	---	---	---	---	---	----	-------------------

# 6: How confident are you that you can do things other than just taking medication to reduce how much your illness affects your everyday life?

Not at all confident	1	2	3	4	5	6	7	8	9	10	Totally confident
----------------------	---	---	---	---	---	---	---	---	---	----	-------------------

# 6.9 Annex 6 – Adherence to SENACA and actual use of SENACA

C1

#### 1: Did you start using SENACA?

(Please tick one box only)

- Yes → go to question T2
- ▶ No → if no: Why did you not start using SENACA?

Reason(s):

2: When did you start using SENACA after receiving it?

(Please tick one box only)

- immediately after receiving it
- in the first week after receiving it
- in the second week after receiving it
- in the third week after receiving it
- later than the third week after receiving it

#### 3a: Has there been a time when you stopped using SENACA?

(Please tick one box only)

- ▶ No  $\rightarrow$  go to question **T4**
- Yes → if yes: Why did you stop using SENACA? Reason(s):

#### 3b: If yes: For how many days did you approximately stop using SENACA? (Please fill in the correct number)

I stopped using SENACA in total for |\_\_| |\_\_| days.

→ go to Question

# 4: During the period you used SENACA, how often did you use at least one function of the system? (Please tick one box only)

- More than once per day
- 🕳 Daily
- Twice to six times per week
- Once a week
- Two to three times per month
- Once per month

Less often

#### 5: During the period you used SENACA, how many hours per week did you spend using SENACA on average?

(Please fill in the average number of hours per week)

On average, I used SENACA |\_\_\_ | hours per week.

# 6: Below you find a list with the several elements of SENACA. Which elements did you use? And how many times per week?

(Please mark every element you used and fill in how often you used it on average per week)

#### Type of element

-	Personal health plan	<pre>limes per week.</pre>
	Personal health statistics	<pre>   times per week.</pre>
-	Recipes & Nutrition information	<pre>   I   times per week.</pre>
-	Physical activity tutorials	<pre>   I   times per week.</pre>
	Disease specific information pages	<pre>limes per week.</pre>

# 7: Below you find a list with the several monitoring devices included in SENACA. Which devices did you use? And how many times per week?

(Please mark every device you used and fill in how often you used it on average per week)

#### Monitoring devices

-	Blood pressure	<pre>   times per week.</pre>		
-	Weight scale	<pre>limes per week.</pre>		
-	Physical activity tracker	<pre>   I   times per week.</pre>		
-	Vitalograph	<pre>   I   times per week.</pre>	-	not applicable
 	Glucose measure	times per week.		not applicable

8: Did you h	ave any problems rel	ated to SENACA during the last 50 days?
🗌 No	Yes, namely:	
→go to ques-		
tion C1		
	_	
9: If yes: Ho the last	w often did those pr 50 days.	oblems occur? Please tell us the approximate occurrence in
Problem:		Average occurrence last 50 days:
	_	
Problem:		Average occurrence last 50 days:
	_	
Problem:		Average occurrence last 50 days:
	-	

Problem:	Average occurrence last 50 days:

## Only for drop-outs:

10: Could you tell us the main reasons why you decided to stop participating in the study?

0.

# 6.10 Annex 7a – Socio-demographics (patient)

1. What is your gender?

		▲	
		Male	Female
2.	Whic	h year were you born?	
3. 4.	(Plea	ase enter the two last numbers of your year of birth)	
		5 .   1     9	
3:	In wh i (Ple	ich country do you live? ase tick one box only)	
	 	Switzerland	
	 	Norway	
	-	Israel	
	-	Other:	

4: Is the language mostly spoken in this country your mother tongue?

(Please tick one box only)

- 🔺 Yes
- 🕳 No

#### 5: What is your current marital status?

(Please tick one box only)

- Married / Civil Partnership
- Separated / Divorced from spouse or civil partner
- → Widowed/ civil partner died
- Never married/ never in a civil partnership, single

#### 6: Do you live alone?

(Please tick one box only)

→ Yes → go to question 7

# → if no: Please tell us how many persons you are living with including yourself:

Total household size: \_\_\_\_\_ persons

Please fill in the table below by indicating the relationship to the persons you are living with, e.g. "Person n°1: Husband; Person n°2: Daughter, ..."

Person Number	Relationship

7: Which person do you consider as the most important caregiver? If the person lives in your household, please enter the number of the person from the table above.

(Please tick one box only)

- Person lives in household: Number |\_\_|
- Somebody who does not live in my household
- 8: How many full years of schooling do you have? Please include primary and secondary schooling, university and full-time vocational training, but do not include repeated years. (Please enter the total number of years)

#### |\_\_||\_\_| Years

#### 9: What is the highest level of education that you have attained?

(Please tick one box only)

- No formal education
- Primary school
- Lower Secondary (end of obligatory school; does not allow entry to university)
- Upper Secondary (allow entry to university)
- Post-Secondary, non-tertiary (vocational training)
- Lower level tertiary (Bachelor degree, also technical schools)

Logical Structure Upper level tertiary (Diploma, Magister, Master degree, doctor)

#### 10: What is your current work status?

(Please tick one box only)

- Employed
- Unemployed
- Self-employed
- Student/ scholar
- Retired
- Houseman/-wife
- Lunable to work due to illness
- Other:
- 6. (Please enter the total number of years)
- 7.

8. |\_||\_| Years

9.

10.

#### 11: Which of the following three chronic diseases do you have?

(Please tick each box that applies to you)

- Heart disease (chronic heart failure)
- Diabetes (Diabetes mellitus)
- Lung disease (chronic obstructive pulmonary disease)

#### 12: Since how many years and months is this disease diagnosed?

(Please enter the exact number of years and months. If you don't remember the exact number please try to estimate. If you have ticked more than one box in E1, please refer to the disease that was diagnosed first)

Years	Months
13: Did you have hip and/or kr	nee replacement?
(Please tick one box only)	
L	L.
No	Yes

14: If you had hip or knee replacement, how many days passed by since that surgery? (Please enter the exact number of days. If you don't know the exact number please try to estimate)

Days |\_\_||\_\_|

# 15: Apart from the diseases you reported in the questions before, which other diseases do you have?

(Please tick each box that applies to you)

- Lancer
- Mental disease
- Musculoskeletal diseases (Rheumatism, Osteoporosis, Arthritis, Spinal cord, back pain)
- 🔺 Asthma
- 🗕 Fibromyalgia
- Severe allergy
- Multiple sclerosis
- Neurological disease (incl. Parkinson's and dementia)
- Hypertension
- 🗕 Emphysema
- Gastrointestinal diseases (incl. Crohn's disease)
- Other

# 6.11 Annex 7b – Socio-demographics (caregiver)

#### 1: What is your gender?

(Please tick one box only)

▲ Male  Female

#### 2: Which year were you born?

(Please enter the two last numbers of your year of birth)

|1| |9||\_\_||\_\_|

#### 3: In which country do you live?

(Please tick one box only)

- Switzerland
- 🕳 Norway
- 🔺 Israel
- L Other: \_\_\_\_\_

## 4: What is your current work status regarding the main amount of hours you spend on?

(Please tick one box only)

- Employed
- Unemployed
- Self-employed
- Student/ scholar
- Retired
- Houseman/-wife
- Unable to work due to illness or accident
- Other: \_\_\_\_\_

#### 5: What is your relation to the person you care for?

(Please tick one box only)

- Partner
- Parent
- Grandparent
- Sibling
- Other family. Please describe: \_\_\_\_\_\_
- Non-family. Please describe:

6: Do you and the person you care for live in the same household?

(Please tick one box only)

- Yes, live together → if yes: go to question X1
- No, live separately

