#### Table 1. Role of involved organizations in USECARE study

#### Participants

Participants in the study are community-dwelling older adults aged 50 years and older living with one or more chronic diseases who are at risk of developing complications and/or destabilization of their chronic conditions (primary end-users) and their informal caregivers (secondary end-users, i.e. spouses, children or other non-family and family members). Study participants are recruited from healthcare organizations in the countries participating in USECARE AAL. Table 2 lists the *inclusion and exclusion criteria*, which are straightforward:

Table 2. Inclusion and exclusion of	criteria for USECARE AAL study.
-------------------------------------	---------------------------------

Community-dwelling older adults (primary end-users)				
Inclusion criteria	
 
receive medical care for one or more of the following chronic diseases in hospital settings and outpatient clinics: 
 
Chronic Heart Failure (CHF, New York Heart Association NYHA II-IIIa);
 
Diabetes Mellitus (DM, 6< HbA1c<9),
 
Chronic Obstructive Pulmonary Disease (COPD, GOLD I-II)
 
Special Orthopaedic Co-Morbidity (SOCM, after elective hip or knee replacement, health status temporarily destabilized respectively challenged, increased monitoring and formal/informal care)
 
having support of an informal caregiver that is aged 18 years or older
 
are aged 50 years and older (community-dwelling older adults, primary end-user)
 
 
 
			
Exclusion criteria	
 
known illiteracy (reading and writing difficulties)
 
lack of local language proficiency
 
lack of internet access
 
current major mental illness of moderate to severe level
 
major acute illness or surgery in past 3 months (except elective hip / knee surgery for patients with SOCM)
 
participation in another intervention study
 
			
Informal caregivers (secondary end-users)				
Inclusion criteria	
 
aged 18 years or older
 
be named by primary end-user as designated informal caregiver providing physical, emotional and/or social support for him or her
 
			
Both older adults and informal caregivers				

Inclusion criteria	•	written informed consent adequate functional, sensory and cognitive abilities to use the SENACA system

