#### 2.2.5 Variables and Measurements

To evaluate the usability (Part I) and evolution of various parameters hypothesized to be responsive to the enhanced SENACA prototype (Part II), the following variables will be addressed and measured with measurements listed in table 3 (additional information on parameters and questionnaires is also listed in the annex section):

Parameters	Mode	Variable	Description	Definition
	Self-reported	Age		Year of birth
		Sex		Sex of participants
Socio-demographics		Education		Number of years in education and highest degree
		Work status		Work status
		Marital status		Legal status
		Cohabitation		Living arrangement
		Nationality		Nationality of respondent & Language skills
		Caregiver relation		Person who is considered as the most important caregiver

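### The caregiver-relation item has no child option and its generational options run against its question, and the patient form records no relation for a caregiver living elsewhere

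*Protocol*

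**What the plan says.** Section 2.2.2 (Participants) describes the informal caregivers as "secondary end-users, i.e. spouses, children or other non-family and family members". Table 2 requires patients to be 50 or older and caregivers 18 or older.

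Table 3 (section 2.2.5) lists "Caregiver relation" among the socio-demographic variables and defines it as "Person who is considered as the most important caregiver".

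Two questionnaires bear on it:

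- **Caregiver form, Annex 7b item 5.** The question is "What is your relation to the person you care for". The answers are Partner, Parent, Grandparent, Sibling, and two write-in options, one of them "Other family. Please describe" and the other for non-family.
- **Patient form, Annex 7a items 6 and 7.** A patient who does not live alone is told: "Please fill in the table below by indicating the relationship to the persons you are living with". Item 7 then asks for the most important caregiver. A co-resident caregiver is identified by their number in that table. Any other caregiver is recorded by one tick box, "Somebody who does not live in my household", with no field for the relation.

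**The concern.** An item that records a family relation has to fix its direction: what the caregiver is to the patient, or what the patient is to the caregiver. Here the question points one way and the generational options point the other. The answer that an adult child would give to the question as worded is not on the list. Two daughters in the same position can then give different answers, both in good faith.

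The patient form would be the natural cross-check, but it gives no relation when the caregiver lives elsewhere.

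What is at stake is the description of who the caregivers were. Usability from the caregivers' perspective is part of objective Ia (section 2.1.1), and the study is mainly descriptive with a small sample (section 2.2.8). A table of caregivers by relation is an ordinary part of such a report.

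**Working it through.** The protocol states no figure on this point. The check sets the two forms side by side, with a short age calculation to see which reading the options fit.

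**1. Which direction do the options fit?** Inputs: patient at least 50 and caregiver at least 18 (Table 2). Assumption: 18 to 25 years per generation.

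| Option | Question as worded: caregiver is the patient's ... | Reversed: patient is the caregiver's ... |
|---|---|---|
| Parent | caregiver at least 50 + 18 = 68 (50 + 25 = 75) | patient at least 18 + 18 = 36 (18 + 25 = 43); met by every patient |
| Grandparent | caregiver at least 50 + 2 × 18 = 86 (50 + 2 × 25 = 100) | patient at least 18 + 2 × 18 = 54 (18 + 2 × 25 = 68); plausible |

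Read as worded, Grandparent is practically empty and Parent would be rare. Read in reverse, both are ordinary answers. Partner and Sibling are symmetric and unaffected.

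**2. Where does a son or daughter go?**

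- Following the question: no box fits, so they use the write-in for other family and can enter son or daughter. The record is correct.
- Following the list: they tick Parent. The record is correct on the reversed reading and wrong on the literal one.

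The same relation can therefore sit in two codes. A grandchild faces the same choice between Grandparent and the write-in.

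**3. Does the patient form settle it?** The household table's own examples (a husband, a daughter) record what the other person is to the patient. That is the opposite direction to a Parent tick on the caregiver form.

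- Co-resident caregiver named in item 7: the table gives the relation, so an ambiguous tick can be checked.
- Caregiver living elsewhere: no relation is recorded. This includes the caregiver of every patient who lives alone, because item 6 sends those patients straight to item 7 without the table.

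**4. What can other items recover?** Year of birth is item 2 on both forms. A Parent tick from a caregiver younger than the patient points to a child, and from an older one to a parent. The write-in text resolves the other-family answers where it is completed. Both routes have limits: comparing birth years requires the two forms to be paired, which the protocol does not describe, and it cannot separate a child from a child-in-law who ticked Parent.

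**The case against.** The strongest case on the other side is that this is a wording flaw in one background item. The write-in option lets a child be recorded exactly, and birth years usually reveal what a Parent tick means. Patients are recruited together with a designated caregiver, so pairing the forms is feasible. For an enrolled caregiver, Annex 7b item 5 supplies the relation wherever they live, so the gap on the patient form is a missing second source. The local-language versions are not shown and may not share the ambiguity. Most of this stands, and it is why the point is minor. It does not remove the conflict between question and options, or the blank on the patient form.

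A reader might infer four stronger things that the documents do not support:

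- **That the relation is miscoded, or that every child caregiver is affected.** Those who write in their relation are recorded correctly. The fault is an unfixed direction, which permits misclassification without making it certain.
- **That a planned analysis is damaged.** Section 2.2.8 plans descriptions for carers and patients and compares module use across user groups. It announces no breakdown by spouse versus child, and no outcome uses the item.
- **That relation is needed because age and familiarity with technology drive use.** The background section on technology acceptance says only that such characteristics may affect use, and it also cites studies that found no age effect. Caregiver age is measured directly.
- **That asking for the most important caregiver, when a designated caregiver is enrolled, contradicts the stated variable.** Item 7 matches the Table 3 definition. The two people need not coincide, but the item collects what Table 3 defines.

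**Conclusion.** The point holds as a low-impact instrument error. Annex 7b item 5 does not fix the direction of the relation and has no box for a caregiver group the protocol names, so child caregivers may be divided between Parent and other family according to how each reads the item. On the patient form, the relation of a most important caregiver living outside the household is not collected, although Table 3 lists caregiver relation.

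The consequence is limited to describing the caregiver sample. No proportion affected can be given: the documents state neither the expected share of child caregivers nor the share living apart from the patient. Recovery is partial and depends on completed write-in text and paired forms.

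The age argument assumes 18 to 25 years per generation and does not change across that range. The judgement rests on the English wording in the annexes.

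**What to change.** - **Annex 7b item 5:** make question and options run in one direction. Either reword the question so that the respondent completes a sentence stating what the person cared for is to them, and keep the present options; or keep the question and add son/daughter and grandchild options. Apply the same direction in all local-language versions.
- **Annex 7a item 7:** add a relationship line to the answer for a caregiver outside the household.

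The cost is rewording one item and adding one line to another in the baseline questionnaires, with negligible burden on respondents. It should be done before the forms go out. If forms are already in use, pairing patient and caregiver forms and reading birth years with the write-in text would recover part of the information.
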